ALTA is a health systems approach to improving medication adherence and BP control in primary care practices. It is designed to build practice capacity to address the needs of hypertensive patients by utilizing a team-based approach to delivering HTN care. ALTA includes five key components, which are conducted by existing members of the practice (Table 1): (1) Identify ALTA-eligible patients using hypertension registries. (2) Refer ALTA patients to a clinic Health Coach using the EHR. (3) Coach ALTA patients using a structured counseling tool integrated in the EHR to identify patients' treatment goals; assess their current level of BP control and medication adherence; identify barriers and facilitators to medication adherence; develop patient-centered adherence goals and action plans; and use a structured treatment algorithm to optimize patient antihypertensive medication regimen. (4) Document brief progress notes from the coaching session in the EHR to inform other team members of the patient's adherence status, action plans, progress toward goals, and any changes to the antihypertensive medication regimen. (5) Monitor and schedule follow-up sessions with ALTA patients in the EHR.

Table 1. ALTA components

ALTA components	ALTA Activities
Identify and Refer	
 • EHR registry to identify patients with uncontrolled HTN and non-adherent • EHR-based referral to MA/PCA/RN
Coach	
 • Structured assessment of medication adherence • Use of MINT to identify facilitators/barriers to adherence and discuss personalized strategies to improve adherence behaviors • Use of structured medication titration algorithm to optimize patient treatment regimen • Use of teach back to ensure patient understanding of treatment plan • Co-creation of culturally relevant goals and action plans
Document	
 • Structured documentation of coaching sessions in EHR to enable tracking patients' progress over time • EHR Documentation of individualized treatment plan, medication adherence goals, and action plan to guide future sessions and share with primary care provider for clinic visits
Monitor	
 • Consistent monitoring of patient progress through completion of and tracking follow-up sessions with ALTA patients

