Tertiary outcomes will include measures of the patient-provider relationship- relationship commitment, patient-provider trust, patient anxiety in the interaction, patient trust in healthcare, discrimination in medical setting, Health literacy, health intake, and patient trust in medical technology at the pre-intervention (baseline) and post-intervention (12 month) periods.

Relationship commitment: In this study, we operationalize relationship commitment as patients' commitment to maintain care with their PCP when ALTA is introduced into their site. To assess patients' *perceived commitment* to their PCP, we will utilize the self-report measure developed by Berry et al. in a sample of primary care patients. The 5-item measure asks patients to rate their degree of commitment to the relationship with their doctor on a 7-point Likert scale (*strongly disagree* to *strongly agree*). Sample items include: *The relationship with my doctor is...something I am committed to; something I care about; and important to me.* To assess the *behavioral and affective indicators* of relationship commitment we will use natural language processing (NLP) and analyze text of patient-provider interactions that occur in the 12 months prior to ALTA, and over the 12 months ALTA phase. Data will be extracted from the EHR (e.g., clinical notes, messages, and free text) and MyChart to conduct these analyses.

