Level of implementation adherence will be evaluated quantitatively as the degree to which the components of ALTA (e.g., identify, refer, coach, document, monitor) were implemented as intended, using data from checklists completed by the facilitators as well as extracted from the EHR. Each intervention component will be rated on a 3-point scale: 1=The component was not implemented, as per protocol; 2=The component was partially implemented; and 3=The component was fully implemented and/or modified with permission, as per protocol. We will calculate adherence as the number of components fully implemented (ratings of 3) divided by the total number of possible components (N=8). Practices will be considered adherent to the protocol if components were implemented completely and/or they were completed with an adaption that did not affect the programs core components and was approved by the study team. Facilitators will also complete monthly narrative reports that summarize all adaptations made to the components and what did/did not work for each practice context. We will also measure adherence through the Health Coaching Evaluation Checklist. The checklist will be used to count the parts of the standardized counseling script that were covered by the MAs at each health coaching session.

Implementation dose will be evaluated as the extent to which patients were exposed to ALTA. We will collect data on utilization patterns of the different ALTA components including the mean number of: ALTA-eligible patients identified in the registry and referred to a Health Coach; health coaching sessions completed with ALTA patients; entries in the EHR-embedded coaching script; progress notes documented in the EHR and shared with the care team; and follow-up sessions that are scheduled and/or completed. System files will be extracted quarterly and will contain date and time stamps as well as user logins for the tools used.

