Maximum likelihood estimation of mixed-effects models will be used to account for missing data; this is equivalent to an assumption of data missing at random. We will conduct sensitivity analyses assessing this assumption. We will also compare participants with and without missing values in baseline and site characteristics, as well as intervention vs control group status; if differential patterns emerge, we will consider using multiple imputation and/or inverse probability weighting to adjust for missing data. For our behavioral measures of commitment and trust derived from text analysis, we will use Python with a dedicated suite of libraries for sentiment analysis and emotion detection. The text processing libraries will be used to complete the pre-processing steps including tokenization, stemming, and lemmatization. Tokenization is the process of separating text into smaller units, i.e., words, characters, or subwords. Stemming and lemmatization will be done to reduce inflectional forms and derive the common base form [e.g., am, are, is → be]. Next, each document (clinical notes, transcripts, secure messages) will be represented as vectors using word embeddings. Distributional semantics models (e.g., continuous Bag-of-Words, Skip-gram, Global vectors) will be used to represent each word as a vector while preserving the contextual information of the word before the training phase. Resources such as lexicons (e.g., LIWC, EmoLex) will be used for feature extraction representing presence or absence of emotion words, and words associated with opening or closing rituals of a conversation. Next, multiple supervised and unsupervised algorithms (e.g., attention-based neural models, transformers architecture) will be trained on the dataset and an optimized model will be established via several rounds of experiments and rigorous evaluations. Once the best fitting model is established, it will be used to train on clinical notes data before and after ALTA implementation. Patient and providers' sentiment will be compared to establish how the relationship has changed through ALTA participation. we will use GLMM to analyze the effect of ALTA on the tertiary outcomes of patient state anxiety, SBP, DBP, and PDC. Since each individual outcome is of interest, testing will be 2-sided with a Type I error rate of 0.05 and no adjustment for multiple testing.

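### The before-after text comparison in 6.4.3.3 does not separate out ALTA-generated notes, so the text-derived commitment and trust indicators can shift from documentation alone

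*Combined protocol and SAP*

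**What the plan says.** Section 5.2.2 defines the behavioural and affective side of relationship commitment through natural language processing. The plan is to "analyze text of patient-provider interactions that occur in the 12 months prior to ALTA, and over the 12 months ALTA phase". On sources it says: "Data will be extracted from the EHR (e.g., clinical notes, messages, and free text) and MyChart to conduct these analyses". Behavioural indicators of trust come from notes and secure messages in the same way (5.2.2, 6.1.4).

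Section 6.4.3.3 describes the processing. Text is tokenized and reduced to base word forms, then "each document (clinical notes, transcripts, secure messages) will be represented as vectors using word embeddings". Lexicon features are extracted and candidate models are trained. Of the best model it says "it will be used to train on clinical notes data before and after ALTA implementation". The inference follows directly: "Patient and providers' sentiment will be compared to establish how the relationship has changed through ALTA participation".

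ALTA changes what is written in that same record. One of its five components in 3.2 is "Document brief progress notes from the coaching session in the EHR", and Table 1 there lists "Structured documentation of coaching sessions in EHR to enable tracking patients' progress over time". The dose measure in 6.1.4 counts entries in the EHR-embedded coaching script and "progress notes documented in the EHR and shared with the care team". Section 6.1.4 also describes an ALTA workflow built in Epic, with physicians as well as MAs and RNs among the users of its template.

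**The concern.** A before-after comparison of chart text measures the relationship only if the charting is comparable in both windows. Here the intervention is partly a documentation intervention. It introduces note types that did not exist before, and 6.1.4 treats good completion of the templates as part of implementation quality. If those notes enter the scored text and score differently from ordinary notes, the average moves even when patients and providers relate exactly as before.

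Two conclusions are at stake. The first is the statement about how the relationship changed through ALTA. The second is the tertiary objective in 4.4 that links relationship change to change in adherence and BP. If the text-derived scores are used there, a score that moves with the number of coaching notes is partly a measure of ALTA dose, and a dose association could be reported as one running through the relationship.

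**Working it through.** The plan gives no sample size, effect size, text volume or ALTA share of text for this comparison, so there is no figure to reproduce. The check is mainly a comparison of sections, followed by an illustration.

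**1. Is there a corpus rule?** Sections 5.2.2, 6.1.4 and 6.4.3.3 name sources and windows. None restricts note type or author, removes template strings, or holds the document mix constant. The pre-processing in 6.4.3.3 works on words, not on document types.

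**2. Is ALTA text confined to one window?** Yes. Section 6.1.1 states that ALTA is not implemented during usual care, so script entries, coaching notes and ALTA template text belong to the later window.

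**3. Does the added text overlap with what is scored?**

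| Scored from text (5.2.2, 6.1.4) | Recorded by ALTA (3.2) | Overlap |
|---|---|---|
| Trust: patient disclosure of problem behaviour, with non-adherence as the example | Structured adherence assessment; adherence status in the progress note; patients selected for adherence below 80% (5.3.2) | Clear |
| Commitment: agreement on a plan, closing language | Goals and action plans | Plausible |
| Commitment: warmth, questions, tentative words, negative affect | Template wording is not in the documents | Unknown, could go either way |

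**4. Do other parts of the plan remove it?** The control-group indicator in 6.4.3.3 is stated for the mixed model, not for the text comparison. Controls in the final analysis are patients who declined ALTA throughout, so they should have no coaching notes; contrasting them with ALTA patients would keep the artefact. The exit interviews (30 patients, 30 staff) take place at 12 months only and cannot calibrate a before-after shift.

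**5. Illustration A: a yes/no disclosure indicator.** Let p0 be the share of patients with disclosure found in ordinary notes, unchanged over time. Let c be the share with a coaching note that the scoring counts as disclosure, taken as independent of p0. Both are assumed. After value = p0 + c(1 − p0).

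| p0 | c = 25% | c = 50% | c = 75% |
|---|---|---|---|
| 10% | 32.5% | 55% | 77.5% |
| 30% | 47.5% | 65% | 82.5% |
| 50% | 62.5% | 75% | 87.5% |

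For example, 0.30 + 0.50 × 0.70 = 0.65.

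**6. Illustration B: a mean score.** If a share w of later text is ALTA documentation scoring d SD away from ordinary notes, the mean shifts by w × d with no true change.
- Assumed: w, d, and an SD of 1 for the patient-level difference.
- Borrowed from the plan: n = 700 with m = 70 per clinic (the survey sample); ICC 0.01 to 0.05 (stated for BP control in 6.4.2); two-sided 0.05 (the level in 6.4.3.3, not tied to the sentiment comparison). ICC 0 is added for reference.
- DE = 1 + (m − 1) × ICC = 1, 1.69, 4.45. SE = √(DE/n) = 0.0378, 0.0491, 0.0797.
- P(reject) = Φ(wd/SE − 1.96) + Φ(−wd/SE − 1.96).

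| w | d | Shift | ICC 0 | ICC 0.01 | ICC 0.05 |
|---|---|---|---|---|---|
| 0 | any | 0 | 5% | 5% | 5% |
| 0.1 | 0.2 | 0.02 | 8% | 7% | 6% |
| 0.2 | 0.5 | 0.10 | 75% | 53% | 24% |
| 0.3 | 0.5 | 0.15 | 98% | 86% | 47% |
| 0.3 | 1.0 | 0.30 | 100% | 100% | 96% |

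The result is symmetric in the sign of d. The only volume figure in the plan, 800,000 annual visits over 125,000 patients or 6.4 per patient (5.3), covers the whole network. It does not count notes for hypertensive patients, so I do not derive w from it.

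**The case against.** The strongest reply is that the scope is already narrower than it looks. Section 5.2.2 targets interactions between patient and provider and defines commitment as toward the PCP. The example table in 6.1.4 describes PCP-patient exchanges throughout, while coaching is referred to MAs, PCAs or RNs. The before-after sentence names clinical notes, not every source. Coaching notes may therefore be meant to fall outside. This stands in part: a reader might infer that the plan pools all chart and message text, and it does not say so. But the intended scope is never turned into an extraction rule, and an author rule alone would leave ALTA template text in physician notes.

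Other objections stand as limits:
- A reader might infer that ALTA also adds templated patient messages. None is described. The nearest item in 6.1.4 is a prompt for physicians to place a MyChart home BP monitoring order, and the scripted MyChart messages in 6.3.4 are for recruitment.
- The perceived-commitment and trust questionnaires are not altered by note templates.
- A brief structured note could lower warmth or question scores, so a rise is not established.
- Training on text from both periods is not in itself a bias. Freezing the model on pre-ALTA text would be a modelling preference.
- Section 6.4.3.3 does plan to compare interview transcripts with the text results as evidence of validity. That may expose a discrepancy, but it does not correct one.

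**Conclusion.** The concern holds for the text-derived commitment and trust indicators. Followed as written, 6.4.3.3 cannot tell a change in charting from a change in the relationship. The case is strongest for disclosed non-adherence and plausible for agreed plans.

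A reader might go further and say that the relationship scores must rise by construction. The documents do not support that: a shift occurs only if ALTA text enters the corpus and scores differently from ordinary notes, and neither its size nor its direction can be found from the plan. The illustrations span a negligible effect (6% to 8% rejection against a nominal 5%) to near-certain rejection (96% to 100%), entirely according to the assumed w and d. They show why a rule is needed and are not estimates. These are tertiary outcomes with survey measures alongside, so the primary and secondary conclusions are not affected by this point.

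**What to change.** In 6.4.3.3, define the corpus for the main before-after comparison:
- Use the same document types and authors in both windows: PCP-authored notes and patient-PCP messages.
- Exclude ALTA coaching scripts and coaching progress notes, and strip ALTA template and smart-text strings from the remaining notes.
- Apply one identical scoring model to both periods.
- Compare per-document rates, so that a change in note volume does not count as a change in content.
- Report ALTA-generated text separately as a sensitivity analysis.

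The cost is added SAP wording, a note-type and author filter in the extract with a list of template strings, and fewer scored documents. No new data collection is needed.

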Adherence to antihypertensive medications (secondary outcome)	
 Proportion of days covered metric based on pharmacy refill data EHR 	
 EHR Voils Adherence Measure 	Baseline and 12 months
Patient-provider relationship	
 Perceived strength of relationship commitment Level of mutual trust between patients and providers Level of patient anxiety in the interaction 	
 EHR MyChart Survey 	Baseline and 12 months (survey) Ongoing (EHR and MyChart)
Semi-structured interviews			
Exit interview	
 Moderator's guide that inquiries about satisfaction and recommendations for improvements as well as impacts of ALTA on the patient-provider relationship 	
 Interviews with 30 clinical and nonclinical staff across all sites Interviews with 30 patients across all sites 	12 months

An outcomes assessment is completed at the Implementation Phase Study Visit at 12-months, including surveys about satisfaction with the intervention and implementation process at each site. A set of questions measuring potential ripple effects and capacity for sustainability will be assessed at this time at FGP practices as part of the 12-month Online Survey, and is described below. We are completing these questions at FGP practices only to understand sustainability considerations within these practices. Questions take less than 10 minutes to complete.

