6.4.3.3. Tertiary Outcomes

We will use Generalized Linear Mixed Model to analyze the effect of ALTA on differences in relationship commitment (primary outcome) and patient-provider trust (secondary outcome). A Poisson regression model will be used specifying a fixed effect for time, a fixed effect for treatment, a time by treatment interaction, and a control group indicator. Only patients that declined participation in ALTA for the entire evaluation period will be included in the control group for the final analyses. Patients that crossover from the control group to intervention group and continue to participate in the evaluation will be counted towards the intervention group sample. Since they are asked the same questions, it does not impact the analyses. Random effects will be specified for person and clinic to account for the clustered nature of the dataset (observations within person and people within clinics). Relationship commitment will be defined as a continuous variable while patient-provider trust will be categorized as ordinal. Randomization of the stepped wedge design should obviate the need for adjustment, but in the case of imbalance in baseline covariates, these will be included as necessary in adjusted analyses. Sex will be accounted for as a covariate and examined as a potential moderator. All tests will be two-sided with $\alpha=0.05$ for comparison between the ALTA and UC phases.

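### The text-derived commitment and trust measures have only a before-versus-after-ALTA comparison stated, so a change over time shared by all practices could be read as an effect of ALTA

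*Combined protocol and SAP*

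**What the plan says.** Sections 5.2.2 and 6.1.4 define relationship commitment and patient-provider trust each in two ways: by survey scale, and by indicators taken from text. For the commitment indicators the plan will "analyze text of patient-provider interactions that occur in the 12 months prior to ALTA, and over the 12 months ALTA phase"; trust is to be handled in the same manner. Table 2 in 6.1.4 lists the surveys at baseline and 12 months, and the EHR and MyChart text as collected on an ongoing basis.

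Section 6.4.3.3 has three parts that matter here.

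- It opens with a mixed model for relationship commitment and patient-provider trust, "specifying a fixed effect for time, a fixed effect for treatment, a time by treatment interaction, and a control group indicator", with random effects for person and clinic. It adds: "Relationship commitment will be defined as a continuous variable while patient-provider trust will be categorized as ordinal".
- It then turns to text as a separate matter: "For our behavioral measures of commitment and trust derived from text analysis, we will use Python with a dedicated suite of libraries". After the language-processing steps, the chosen model is described so: "it will be used to train on clinical notes data before and after ALTA implementation". The comparison that follows is "Patient and providers' sentiment will be compared to establish how the relationship has changed through ALTA participation".
- It closes with a second mixed-model list: state anxiety, SBP, DBP and PDC. The text scores are not on it.

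**The concern.** The one comparison attached to the text scores is before against after, and the difference is attributed to ALTA. No calendar-time term, practice effect or concurrent comparator is named for it. If portal use, note-writing habits or the mix of visits shifted in all practices over the study years, sentiment would move in every practice whether or not ALTA did anything.

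At stake are the tertiary objectives in section 4.4: the impact of ALTA on the patient-provider relationship, and whether changes in that relationship go with changes in adherence and BP control. The trial is a stepped wedge and text is captured continuously, so the design already holds the information needed to separate ALTA from calendar time. The stated comparison does not use it.

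**Working it through.** The plan gives no effect size, SD, trend or power for the text scores, so there is no figure of its own to reproduce. The power figures in 6.4.2 concern BP control.

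**Step 1. What the before-after difference estimates.** The windows are centred 6 months before and 6 months after ALTA start. Their midpoints are 12 months apart in every practice, whatever its wave. With ALTA effect θ and a shared linear trend β per year:

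E(after − before) = θ + β × 1 year.

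Staggering does not remove β unless calendar time is in the model.

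**Step 2. Whether the design can separate them.** Figure 1 is read as five cohorts on 3-month steps, with a 6-month pre-implementation phase and 12 months of ALTA:

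| Cohort | 12 months before (quarters) | ALTA (quarters) |
|---|---|---|
| 1 | 1–4 | 5–8 |
| 2 | 2–5 | 6–9 |
| 3 | 3–6 | 7–10 |
| 4 | 4–7 | 8–11 |
| 5 | 5–8 | 9–12 |

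Cohort 5's before year is cohort 1's ALTA year. With 10 practices and 8 quarters each there are 80 practice-quarters. The parameters are 10 practice effects + 11 quarter effects + 1 ALTA effect = 22, and the design matrix has rank 22. If the before window keeps only its two usual-care quarters, 10 × 6 = 60 practice-quarters remain. The rank is still 22, but the concurrent comparison then rests on quarters 5–6.

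**Step 3. Illustrative size.** Assumptions, none from the documents: total SD 1, clinic variance 0.05, patient variance 0.45, residual variance 0.50 per quarter, a linear trend identical in all practices, and no ALTA effect. The 10 practices and 70 patients per practice are from the protocol.

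Before-after standard error: each window averages 4 quarters, so the variance per patient is 0.50/4 + 0.50/4 = 0.25. Over 700 patients, √(0.25/700) = 0.019 SD.

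| Drift (SD per year) | Patient-level z-test | Practice-level t-test (10 means) | Calendar-quarter model |
|---|---|---|---|
| 0 | 4.9% | – | 4.9% |
| 0.02 | 17.5% | 15% | near 5% |
| 0.05 | 76.6% | 66% | 5.0% |
| 0.10 | 100% | 99.7% | 4.5% |

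The mean before-after estimate was 0.051 SD at a drift of 0.05 and 0.100 SD at a drift of 0.10, as Step 1 predicts. The calendar-quarter model gave 0.000 to 0.001 SD.

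**Step 4. Sensitivity.** With one score per patient per window instead of quarterly scores, the z-test rejects in 26% and 75% of runs at drifts of 0.05 and 0.10. If practice trends vary with SD 0.10 per year around a mean of 0.05, the practice-level test falls from about two thirds to 23%.

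**Step 5. Price in precision.** The calendar-quarter model has a standard error of about 0.040 SD, and 0.040/0.019 = 2.1 times the before-after value. With usual-care quarters only it is about 0.072 SD: 0.072/0.019 = 3.8 times the full-window before-after value. Against a before-after contrast on the same restricted data, √((0.50/2 + 0.50/4)/700) = 0.023 SD, the ratio is 0.072/0.023 = 3.1.

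**The case against.** The strongest reply is that the opening model of 6.4.3.3 already covers this. It names commitment and trust, and sections 5.2.2 and 6.1.4 define both to include text indicators. It carries time, treatment, interaction and control-group terms and appeals to the stepped-wedge randomisation. On that reading the later paragraph says only how text is scored. This reply stands in part: the time term is missing by silence, and nothing rules one out. It does not settle the point, for three reasons.

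- The wording fits the surveys. Trust is ordinal, and crossover is said not to matter because both groups answer identical questions. The text measures then get their own paragraph and their own comparison.
- Time is not defined as calendar time. The surveys are taken at baseline and 12 months, and the one explicit coding of time, in 6.4.3.1, is 0 and 12 months.
- The control group is patients who declined ALTA throughout. They are self-selected and do not supply the randomised contrast between practices in and not yet in ALTA.

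Three stronger readings are tempting and not supported.

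- A reader might infer that the plan specifies an uncontrolled significance test. It gives no test statistic or p-value for sentiment, so the rejection rates above belong to tests chosen for illustration. The plan also uses the text results alongside the exit interviews to judge the validity of the sentiment scores, which is an exploratory use.
- A reader might infer that drift is documented. The COVID-19 passages concern research procedures such as consent, interviews and site observation. They do not report changes in clinical notes, messaging or visit mode.
- A reader might infer that the main results are at risk. They are not.

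**Conclusion.** The concern holds in limited form. Followed as written, the text comparison could report a shared secular change as an effect of ALTA, and the only nearby model that might prevent this is not clearly applied to text scores or to calendar time. The direction of the problem follows from the window definition alone: one year of any shared linear trend enters the estimate. Its size cannot be obtained from the documents. The rejection rates rest on assumed drift, variances, quarterly scoring and common trends, and they change materially when those change.

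Calendar-quarter effects would remove only what is common to practices. Changes in note templates brought in by ALTA itself would remain in the ALTA coefficient. The point concerns tertiary measures. It merits a change of wording before the text is analysed.

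**What to change.** Amend 6.4.3.3 to state, for the text-derived commitment and trust scores:

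1. All text is scored with one language model fixed across periods, so that before and after scores are on the same footing.
2. Scores are aggregated to patient-quarter.
3. They are analysed in a mixed model with fixed calendar-quarter effects, an ALTA-on indicator, and random patient and practice effects. The ALTA coefficient is the reported effect.
4. The raw before-after difference is labelled descriptive.
5. How the two pre-implementation quarters are treated. They fall inside the 12-month before window but include staff training and the kick-off event, so that window is not pure usual care.

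Before the period terms are fixed, section 5.1 must be reconciled with Figure 1. The text gives four waves of two sites, which makes 4 × 2 = 8 sites; the figure shows five cohorts, and the protocol has 10 practices. The overlap and rank results above rest on the five-cohort reading.

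The cost is a few sentences and a modest amount of analysis on text already planned for extraction. The real price is precision: on the illustrative assumptions, a standard error of about 0.04 SD against 0.02 SD, or about 0.07 SD if only usual-care quarters form the before window. That loss should be weighed when deciding item 5.
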